7 STATISTICAL METHODOLOGY

7.1 General Considerations

7.1.1 General Principles

For continuous variables, descriptive statistics will include the number of subjects (n), mean, standard deviation, median, minimum and maximum. When needed, the use of other percentiles (e.g.10%, 25%, 75% and 90%) will be mentioned in the relevant section. Frequencies and percentages will be displayed for categorical data. A missing category will be added to categorical variables where data is missing.

Summaries based on ITT (e.g. disposition, baseline and efficacy data) will be presented by planned treatment group, unless specifically stated otherwise. Safety analysis and other summaries based on SAF will be presented by actual treatment received.

All statistical comparisons will be made using two sided tests at the α =0.05 significance level unless specifically stated otherwise. All null hypotheses will be of no treatment difference, all alternative hypotheses will be two-sided, unless specifically stated otherwise.

All data processing, summarization, and analyses will be performed using SAS® Version 9.4 or higher on Windows. Specifications for table, figures, and data listing formats can be found in the TLF specifications for this study.

The Age (Derived) variable from EDC will be used for analysis. If date of birth is incomplete, the variable Age from EDC will be used for analysis.

Year will be calculated as (days/365.25) rounded up to 1 significant digit.

Month will be calculated as (days/30.4375) rounded up to 1 significant digit.

Time to event or duration of event endpoints will be based on the actual date rather than Visit Day.

For the definition of subgroups of interest please refer to section 7.8.

7.1.2 Definitions and Computations

Study Day

Study day will be calculated in reference to the date of randomization (study day 1). For assessments conducted on or after the randomization date, study day is calculated as (assessment date – randomization date + 1). For assessments conducted prior to the randomization date, study day is calculated as (assessment date – randomization date). There will be no study day 0.

Study Day for each line

Study day for each line will be calculated by same definition of "Study Day" replacing the reference date with date of randomization for 1st line AAT, and replacing with date of enrollment for 2nd line AAT respectively.

i.e. when assessment date be included between date of informed consent and date of enrollment for 2nd line AAT - 1 day: (assessment date – randomization date + 1). when assessment date is same or after date of enrollment for 2nd line AAT: (assessment date – date of enrollment for 2nd line AAT + 1)

• Date of First Dose and Date of Last Dose of Study Drug

The date of the first dose of study drug is defined as the date the subject received the first dose of any study drug (enzalutamide or flutamide, whichever comes first). The date of the last dose of study drug is defined as the date the subject received the last dose of study drug (enzalutamide or flutamide).

• Date of First Dose in each line and Date of Last Dose of Study Drug in each line
The date of the first dose of study drug in each line (1st or 2nd line) is defined as the date the subject received the first dose of study drug in each line (enzalutamide or flutamide). The date of the last dose of study drug in each line is defined as the date the subject received the last dose of study drug in each line (enzalutamide or flutamide).

• Treatment Day

Treatment day will be calculated in reference to the date of the first dose of study drug. Treatment day 1 corresponds to the date the subject received the first dose of study drug. For assessments conducted on or after the date of the first dose of study drug, treatment day will be calculated as (assessment date – date of first dose of study drug + 1). There will be no treatment day 0. Study day 1 is not planed date of first dose of study drug, administration will

be started study day 2.

• Treatment-Emergent Period

The treatment-emergent period will be defined as the period of time from the date of the first dose of study drug to 28 days after the date of the last dose of study drug, or 1 day prior to the date of initiation of cytotoxic chemotherapy for prostate cancer or an investigational agent treating prostate cancer, whichever occurs first. And 1st line treatment-emergent period is defined as the period of time from the date of the first dose of study drug in 1st line to 28 days after the date of the last dose of study drug in 1st line, or 1 day prior to the date of initiation of cytotoxic chemotherapy for prostate cancer or an investigational agent treating prostate cancer, whichever occurs first. Regarding 2nd line treatment-emergent period is applied same rule for 2nd line date.

• Baseline Value and Post-Baseline Value

Unless otherwise specified, the baseline value is defined as the last non-missing measurement prior to the randomization of study drug. When analysis be provided separately by treatment lines, baseline value for 2nd line AAT is defined as the last non-missing value measurement prior to the enrollment for 2nd line AAT of study drug.

Post-baseline value is defined as a measurement taken after the randomization of study drug. For Post-baseline value for 2nd line is defined as a measurement taken after enrollment during of study for 2nd line AAT.

Baseline value is defined as the last non-missing measurement prior to randomization (or register of 2nd line AAT) and post-baseline value is defined as a measurement taken after randomization for subjects who did not receive study drug. Change from baseline is defined as (post-baseline value - baseline value). Both date and time of drug administration and measurement should be considered when calculating baseline value. If time is not available, then date only should be used.

Treatment Group

Treatment group is defined as planned randomized treatment sequence which divide to initial enzalutamide 160 mg/day group or the initial flutamide 125 mg × 3 times daily (375 mg/day) group.

• Treatment Arm

Treatment arm is defined as administration drug group regardless 1st line or 2nd line treatment. That is enzalutamide plus ADT arm include subject who receive enzalutamide plus ADT at 1st line and 2nd line. Flutamide plus ADT include who receive flutamide plus ADT at 1st line and 2nd line.

• Treatment Line

Treatment line is defined as 1st line AAT and 2nd line AAT. When analysis by treatment line is provided, divided to data of 1st line AAT and 2nd line AAT, and calculate descriptive summarization or frequency etc.

7.2 **Study Population**

7.2.1 **Disposition of Subjects**

- Number of subjects with informed consent (overall only)
- Number of subjects randomized with discontinued before randomization (overall only)
- Number of subjects randomized, by treatment group and overall
- Number and percentage of subjects in each analysis set, by treatment group and overall
- Number and percentage of subjects in with transition to 2nd line AAT, by treatment group and overall
- Number and percentage of subjects who had discontinued study drug during 1st line AAT to end of 2nd line AAT, by treatment group and overall
- Number and percentage of subjects who had discontinued study drug by primary reason for treatment discontinuation during 1st line AAT to end of 2nd line AAT, by treatment group and overall
- Number and percentage of subjects who had discontinued study drug during 1st line AAT and not transition to 2nd line AAT, by treatment group and overall
- Number and percentage of subjects who had discontinued study drug by primary reason for treatment discontinuation during 1st line AAT, by treatment group and overall
- Number and percentage of subjects who had discontinued study drug by primary reason for treatment discontinuation during 2nd line AAT, by treatment group and overall
- Number and percentage of screening failure subjects for overall
- Number and percentage of subjects who participated in each study visit, by treatment group and overall for the ITT population

A listing of all randomized subjects discontinued from study treatment, by center and by treatment group, the specific reason for discontinuation, and the last dose day and date will be presented.

7.2.2 **Demographic and Other Baseline Characteristics**

Demographic and other baseline characteristics will be summarized by treatment group as randomized for all subjects in the ITT population. Additionally same summaries will be provided for subject in the SAF population.

Descriptive summary statistics will be presented for continuous variables of:

- Age
- Height
- Weight
- Body Mass Index (BMI)
- Baseline serum PSA value
- Baseline lactate dehydrogenase (LDH) value
- Baseline hemoglobin value
- Baseline alkaline phosphatase (ALP) value

- Baseline serum albumin
- Baseline creatinine value

Frequency tabulations will be presented for categorical variables of:

- Age category (grouped as <65, 65 to 74, 75 to 84, ≥ 85 years)
- Baseline ECOG performance status (0, 1, 2, 3/4)
- Baseline brief pain inventory question # 3 (0-1, 2-3, >3)
- History of prior cardiovascular disease (Yes, No)
- Disease stages at randomization (M0/N0, M0/N1, M1)
- Regional Lymph Nodes at randomization (Nx, N0, N1, Unknown)
- Distant Metastasis at randomization (Mx, M0, M1, Unknown)

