1 INTRODUCTION

1.1 Background

Worldwide, prostate cancer ranks second in cancer incidence (2012) [Torre et al., 2015], and ranks second in Japan as well (2011) [Matsuda et al., 2013]. In 2020, prostate cancer is expected to be at the top in male cancer incidence [Sobue et al., 2012].

Since prostate cancer exhibits androgen-dependent growth, androgen deprivation therapy (ADT) by surgical or chemical castration is widely conducted, and is positioned as a main therapy for prostate cancer. GnRH agonists/antagonists monotherapy or combined androgen blockade (CAB) therapy with concurrent anti-androgenic agents is the main stream androgen deprivation drug therapy in Japan [Japanese Urological Association, 2012].

Castration-resistant prostate cancer (CRPC) is prostate cancer that progresses under endocrinotherapy with ADT. In an early ADT, serum prostate-specific antigen (PSA) level decreases and tumor partially regresses in most patients. Even during the resting period, tumor does not grow, and serum PSA remains low. However, some patients exhibit increased serum PSA and the course of radiographic disease progression in spite of the serum testosterone in the castration level. These patients are considered as castration-resistant. However, clinical researches and studies on the molecular profile of such progressive tumor demonstrate that the function of androgen receptor (AR) is maintained in CRPC, and tumor responds to treatment to lower the function of AR, such as blocking androgens and changing anti-androgenic agents. As a secondary endocrinotherapy, treatment can be selected from alternative antiandrogen therapy (AAT), estrogen therapy, corticosteroid therapy, and CYP17 inhibitors. Chemotherapy is selected for metastatic CRPC resistant to existing endocrinotherapy.

Enzalutamide is an anti-androgenic agent that inhibits AR signaling, and was jointly developed by Astellas Pharma Inc. and Medivation Inc. A clinical trial on enzalutamide targeting CRPC started in 2010 in Japan. In March 2014, marketing approval was obtained as the product name Xtandi[®] with an indication for castration-resistant prostate cancer.

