6.2 Safety Variables

Safety will be assessed by evaluation of the following variables:

- AEs (frequency, severity, seriousness, and relationship to study drug).
- Clinical laboratory variables (hematology, biochemistry including liver enzymes and total bilirubin, and urinalysis)
- Vital signs (systolic and diastolic blood pressure, pulse rate)
- **ECOG Performance Status**

AEs will be recorded from time of actually received the study drugs until the Safety Followup visit (28 days after the final treatment with the study drug, start date of cytocidal chemotherapy, or start date of new treatment for prostate cancer, whichever occurs first.). AEs will be assigned on treatment period (treatment arm) according to definition of treatment-emergent period in section 7.1.2. When assigning treatment arm cannot be judged due to starting date and/or end date of AE is missing, such AEs will be assigned on treatment depending on recorded CRF page. However, the AE that recorded as continues from 1st line AAT will be excluded from assignment of 2nd line AAT. TEAE is defined as an AEs observed within above treatment-emergent period or AEs that assigned the treatment arms. The severity of all AEs is to be evaluated by the investigator based on the National Cancer Institute's Common Terminology Criteria for Adverse Events (CTCAE) version 4.0.

A drug-related AE is defined as any AE with at least possible relationship to study treatment as assessed by the investigator or with missing assessment of the causal relationship.

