All analysis of safety will be presented by actual treatment group for SAF, unless specified otherwise. The last non-missing measurement prior to the first dose of study drug will be used as the baseline.

7.5.1 **Adverse Events**

The severity of all AEs is to be evaluated by the investigator based on the National Cancer Institute's CTCAE version 4.0. The coding dictionary for this study will be Medical Dictionary for Regulatory Activities (MedDRA) version 19.1. It will be used to summarize AEs by SOC and PT.

The safety analysis will be performed in the safety analysis set, and summarized by the time of assessment and by the treatment group that actually received the study drugs. The period of onset in the treatment period with the study drug is defined up to 28 days after the final treatment with the study drug, start date of cytocidal chemotherapy, or start date of new treatment for prostate cancer, whichever occurs first. Safety will be assessed by AEs, frequency of treatment discontinuation associated with AEs, and laboratory test value summary statistics. Descriptive statistics, and not inferential statistics, will be used.

The total number of AEs reported will be presented by treatment arm (i.e. enzalutamide v.s. flutamide) and overall total for the SAF. The same analysis will be provided dividing treatment lines. AEs which have occurred during 1st line AAT and 2nd line AAT will be included to analysis. In this 'event level' analyses, all AEs will be counted separately. The following categories will be presented:

- Number of AEs,
- Number of AEs leading to study drug discontinuation,
- Number of drug-related AEs,
- Number of drug-related AEs leading to study drug discontinuation,
- Number of grade 3 or higher AEs,
- Number of grade 3 or higher drug-related AEs,
- Number of serious adverse events (SAEs),

- Number of drug-related SAEs,
- Number of SAEs leading to study drug discontinuation,
- Number of drug-related SAEs leading to study drug discontinuation,
- Number of SAEs leading to death,
- Number of drug-related SAEs leading to death.

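### SAP 7.1.2 keeps the treatment-emergent window open past the start of an approved, non-chemotherapy prostate cancer treatment, contrary to Protocol 7.5, so some later AEs can be attributed to the study drugs

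*SAP*

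**What the plan says.** Four places define when follow-up stops counting towards a study drug.

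- **SAP 7.1.2 (Treatment-Emergent Period).** The period runs from the first dose "to 28 days after the date of the last dose of study drug", or ends earlier at "1 day prior to the date of initiation of cytotoxic chemotherapy for prostate cancer or an investigational agent treating prostate cancer". The same rule is set for the 1st line and 2nd line periods.
- **Protocol 7.5 and SAP 7.5.1.** The AE onset period ends 28 days after final treatment or, if earlier, at the "start date of cytocidal chemotherapy, or start date of new treatment for prostate cancer, whichever occurs first".
- **SAP 6.2, recording.** AE recording stops at the safety follow-up visit, defined there as 28 days, the start of cytocidal chemotherapy, "or start date of new treatment for prostate cancer, whichever occurs first".
- **SAP 6.2, assignment.** "AEs will be assigned on treatment period (treatment arm) according to definition of treatment-emergent period in section 7.1.2". It adds that "TEAE is defined as an AEs observed within above treatment-emergent period or AEs that assigned the treatment arms".

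SAP 7.5.2 also uses the treatment-emergent period, for worst-grade laboratory shifts and for grade 3 or 4 counts. Neither document says which definition prevails.

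**The concern.** The two stopping rules differ in the therapies that trigger them. Protocol 7.5 stops at any new prostate cancer treatment. SAP 7.1.2 stops only at cytotoxic chemotherapy or an investigational agent. Approved hormonal options fall between the two. Protocol 1.1 says of secondary endocrine therapy that "treatment can be selected from alternative antiandrogen therapy (AAT), estrogen therapy, corticosteroid therapy, and CYP17 inhibitors". Estrogens, corticosteroids and CYP17 inhibitors are not cytotoxic chemotherapy, and the protocol presents them as available choices, not as agents under investigation.

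Because SAP 6.2 sends AE assignment to 7.1.2, a programmer who follows it produces a different event set from one who follows 7.5.1. Comparing the safety of the two regimens is the trial's safety objective. An AE that begins after another therapy has started, but is tabulated under enzalutamide or flutamide, blurs that comparison and departs from the protocol's own definition.

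**Working it through.** The plan gives no figure to reproduce here. The check compares the definitions and then counts days.

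**Step 1: triggers side by side**

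| Rule | Time cap | Chemotherapy | Investigational agent | Other new prostate cancer treatment |
|---|---|---|---|---|
| Protocol 7.5, SAP 7.5.1 | 28 days after last dose | start date | start date (as a new treatment) | start date |
| SAP 7.1.2 | 28 days after last dose | day before start | day before start | no trigger |

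**Step 2: which rule operates.** SAP 6.2 points to 7.1.2 both for assigning AEs to a drug and for defining a TEAE. The rule without the last trigger is therefore the operative one.

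**Step 3: excess days after the last dose.** Let an approved, non-chemotherapy agent start d days after the last dose.

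- Protocol 7.5 closes the window at min(28, d).
- SAP 7.1.2 closes it at 28.
- Excess = 28 − min(28, d).

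| d | Protocol 7.5 closes on day | SAP 7.1.2 closes on day | Excess days |
|---|---|---|---|
| 1 | 1 | 28 | 27 |
| 7 | 7 | 28 | 21 |
| 14 | 14 | 28 | 14 |
| 21 | 21 | 28 | 7 |
| 28 | 28 | 28 | 0 |

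The values of d are illustrative, since the documents do not say when the next therapy starts.

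**Step 4: agent started while still on study drug.** If a prohibited agent starts e days before the last dose, Protocol 7.5 closes the window at that start and SAP 7.1.2 closes it 28 days after the last dose. The excess is 28 + e days, which is more than 28. The censoring tables (Protocol 7.10, SAP Table 7-1) already provide for prohibited therapy during the study.

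**Step 5: chemotherapy.** Here SAP 7.1.2 closes at d − 1 and Protocol 7.5 at d. The difference is 1 day, in the opposite direction.

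**Step 6: would the extra AEs be in the database?** The safety follow-up visit is planned before other prostate cancer treatment, but only where possible (Protocol 2.2.1). Footnote 10 of the 2nd line schedule, in both documents, says that without that visit AEs are collected to 28 days after final treatment. It names no stop at new therapy. AEs in the gap can therefore be recorded, and 7.1.2 then assigns them to the study drug.

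**Step 7: the switch between lines.** The 1st line window in 7.1.2 runs to 28 days after the last 1st line dose and is not expressly closed by the first 2nd line dose. If the 2nd line drug starts s days after the last 1st line dose, with s below 28, the two windows overlap for about 28 − s days. SAP 6.2 removes from 2nd line only those AEs recorded as continuing from 1st line. A new AE in the overlap can fall under both drugs.

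**The case against.** The strongest reply is that the SAP states the intended limit twice, in the recording sentence of 6.2 and again in 7.5.1, so 7.1.2 is a drafting outlier with little effect. Several parts of this stand.

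- If recording really stops at new treatment, most such AEs never reach the assignment step.
- Protocol 5.1.3.4 prohibits these agents during study treatment and between lines. For subjects who follow the protocol, the issue is confined to the end of their final study treatment.
- Protocol 1.1 also says that chemotherapy is chosen for metastatic disease resistant to endocrine therapy, and 7.1.2 already covers chemotherapy. The background shows that other options exist, not how often they follow.
- Safety analysis is descriptive, and investigator-assessed drug-related AEs are tabulated separately. The primary endpoint, alpha and power are untouched.

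The reply does not remove the conflict. Footnote 10 collects AEs to day 28 when the visit is missed, whatever therapy has started, and 6.2 then applies 7.1.2 by name.

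A reader might infer three stronger things that the documents do not support.

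- **That a sizeable share of the 200 subjects is affected.** Nothing gives the frequency or timing of the next therapy, or of missed safety visits.
- **That the laboratory shift tables are equally exposed.** Samples come from visits, and a missed safety visit is replaced by a telephone contact that yields no laboratory values. Only an unscheduled or late sample taken after the new therapy began could enter.
- **That start dates of new treatment are available for everyone.** Protocol 5.1.3.2 records concomitant treatment only up to the safety follow-up visit.

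**Conclusion.** Wrong as written. The SAP contradicts Protocol 7.5 and its own 7.5.1, and the cross-reference in 6.2 makes the departing definition the one that is applied. For an approved, non-chemotherapy agent started after the last dose, the excess attribution window is 0 to 27 days per affected subject. It is longer than 28 days if the agent was started on study treatment. The number of subjects and AEs concerned cannot be estimated from the documents.

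The conclusion assumes that the programmer follows 6.2 literally and that at least some AEs are collected after new therapy starts. The missed-visit rule allows this. The effect is on descriptive AE tables, and only marginally on laboratory tables. The change is worth making because it is cheap and restores the protocol's definition.

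**What to change.** Use one end-of-window rule in SAP 6.2, 7.1.2 and 7.5.1, matching Protocol 7.5: the earliest of 28 days after the last dose, the start of cytocidal chemotherapy, or the start of any new prostate cancer treatment.

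- Choose a single convention for start date or day before. Protocol 7.5 uses the start date, so keeping the day before in 7.1.2 would leave a one-day mismatch.
- Apply the same text to the overall, 1st line and 2nd line windows.
- State that the 1st line window closes when the 2nd line drug starts, so that an AE is not counted under both drugs.

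The cost is a short SAP text change with no new procedures or assessments. The small downside is that a few start dates of new treatment may be missing where the safety follow-up visit was missed. The Protocol 7.5 rule already depends on those dates. The SAP should say how such subjects are handled, for example by the 28-day cap alone, and list them.

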7.2.3 Medical History

Summary statistics will be presented for the ITT population and SAF population for numeric variables of:

- Time (months) from initial diagnosis.
- Total Gleason score at initial diagnosis

Frequency tabulations will be presented for categorical variables of:

- Gleason score: primary score + secondary score (< 3 + 3, 3 + 3, 3 + 4, 4 + 3, 4 + 4, 4 + 5, 5 + 4, 5 + 5, other, and missing)
- Total Gleason score category at initial diagnosis (low [2-4], medium [5-7], high [8-10], Unknown or missing)
- Clinical Tumor Stage at initial diagnosis (Tx, T0, T1, T2, T3, T4, Unknown)
- Regional Lymph Nodes at initial diagnosis (Nx, N0, N1, Unknown)
- Distant Metastasis at initial diagnosis (Mx, M0, M1, Unknown)
- PSA progression at study entry (Yes, No)
- PSA doubling time (PSADT)
- Type of disease progression (PSA progression only, radiographic progression with/without PSA progression) at study entry
- Disease localization (bone only, soft tissue only, both bone and soft tissue, and none) at screening
- Target or nontarget soft tissue disease (i.e., at least one target or nontarget lesion per RECIST 1.1) at screening (Yes, No)
- Extent of disease at (bone, lymph node, visceral lung, visceral liver, visceral lung and/or liver, and other soft tissue) screening

In addition, ongoing medical history at randomization which not related to prostate cancer will be summarized by System Organ Class (SOC) and Preferred Term (PT). Medical history ongoing at randomization will be summarized.

